## 3 TRIAL SUMMARY

---

### **Trial Title:**

STATIC - A Randomised Phase III Trial Comparing Intermittent with Continuous Treatment Strategies in Chronic Lymphocytic Leukaemia (CLL)

### **Trial Design**

STATIC is designed with multiple pathways, the 'Randomisation Pathway' and the 'Clinical Need Cohort', which route a participant enters will be determined by their eligibility.

Randomisation Trial: A prospective, national, multicentre, open-label, randomised, controlled, 2-arm, parallel-group, non-inferiority, phase III trial to assess whether patients with CLL on long-term treatment with with a BTK inhibitor, (including ibrutinib) have similar disease control with an intermittent treatment strategy (experimental arm) compared with standard continuous treatment (control arm).

Clinical Need Cohort: A prospective, national, multicentre, open-label, single-arm, non-randomised cohort to assess the safety and overall survival of patients with CLL receiving long-term continuous treatment with ibrutinib.

### **Aims and Objectives:**

The primary aim is to assess whether patients with CLL on long-term treatment with BTK inhibitor, (including ibrutinib) have similar disease control with an intermittent treatment strategy, known as the 'Pausing Ibrutinib' arm compared with standard continuous treatment, the 'Continuous Ibrutinib' arm.

The primary objective is to assess non-inferiority (NI) of the intermittent treatment strategy in terms of time to treatment strategy failure, defined as the first documented instance of active disease (as defined by the 2018 iwCLL criteria) that does not respond to treatment, or death.

The secondary objectives are to assess the following:

- 1) Overall survival
- 2) Toxicity and tolerability
- 3) Cost effectiveness
- 4) Quality of life
- 5) Summative treatment-free interval
- 6) Response to retreatment in intermittent treatment arm
- 7) Time to next treatment for CLL
- 8) Response to next treatment for CLL
- 9) Rate of resistance mutations
- 10) Evolution of resistant sub-clones

### **Hypothesis: Reduced Treatment-emergent Resistance**

We hypothesise that an intermittent treatment strategy using ibrutinib, will reduce treatment-emergent resistance and thus be at least non-inferior to continuous treatment with regards to time to treatment strategy failure whilst reducing resource impact for the NHS and improving quality of life.

### **Number of participants:**

800 participants will be randomised into the randomisation trial over a 6 year period with ~45% coming from ibrutinib-based treatment arms of the front-line CLL trial FLAIR and ~55% receiving ibrutinib off-trial (via NHS access) for previously treated for CLL. An additional cohort of ~30 patients from the ibrutinib-based treatment arms of FLAIR will be enrolled to a non-randomised Clinical Need Cohort to receive continuous ibrutinib.

**Participant population and participant entry pathway:** (Refer to protocol Section 9 for a full list of eligibility criteria).

- To be eligible for randomisation, participants aged at least 18 years with previously treated chronic lymphocytic leukaemia (CLL) will have already been treated in second or subsequent line of therapy with ibrutinib for at least 3 years and be in clinical remission, defined as no palpable lymph nodes, no palpable spleen and absolute lymphocyte count (ALC)  $<5 \times 10^9/L$ , for at least the last 12 months
- For previously treated CLL participants, the entry pathway is to be randomised to either the 'Pausing Ibrutinib' arm or 'Continuous Ibrutinib' arm
- Front-line CLL participants from the ibrutinib-based treatment arms of the FLAIR trial will have completed 6 years of ibrutinib within FLAIR and the following treatment pathways are available:
  - o Randomisation Pathway: Randomised to either the Pausing Ibrutinib or Continuous Ibrutinib arms; participants must be in clinical remission, defined as no palpable lymph nodes, no palpable spleen and absolute lymphocyte count (ALC)  $<5 \times 10^9/L$ , for at least the last 12 months.
  - o Clinical Need Cohort: Continuous Ibrutinib (non-randomised and non-comparative)

### **Clinical Need Cohort: 'Continuous ibrutinib'**

FLAIR participants with progressive disease after completing 6 years of treatment, but prior to entry into STATIC, would not be eligible for randomisation, but can enter the Clinical Need Cohort. The Clinical Need Cohort will enable this group of participants to continue to receive ibrutinib (continuous treatment), either at the recommended starting dose, or the stable reduced dose they were receiving at the end of the FLAIR trial, but will not be randomised.

### **Randomisation Pathway: overview of pausing / resuming and continuous treatment strategies**

To be eligible for randomisation, previously treated participants will have been treated with continuous ibrutinib for at least 3 years and must have been in clinical remission for at least the last 12 months; whereas front-line participants from FLAIR will have been treated for 6 years with ibrutinib in FLAIR and be in clinical remission for at least the last 12 months. Participants will be randomised 1:1 to either intermittent ibrutinib, known as the 'pausing ibrutinib' arm, or continuous ibrutinib treatment.

*'Continuous ibrutinib' arm*

Participants randomised to continuous treatment will receive ibrutinib (oral) 420mg per day (or other reduced dose, if that dose has been stable for the past 6 months and there are no unresolved toxicities) until strategy failure, defined as active disease as per 2018 iwCLL criteria, death, or the end of the trial.

*'Pausing ibrutinib' arm*

Participants randomised to the 'pausing ibrutinib' arm (intermittent treatment strategy) will pause ibrutinib treatment immediately following randomisation, and restart when the restart criteria are met. When treatment restarts, participants restart ibrutinib treatment at the standard dose (or their previous stable reduced dose) until the treatment pausing criteria are met. The pausing and resuming criteria are assessed locally every 3 months at standard clinic visits. Participants can pause and restart treatment multiple times until treatment strategy failure (defined as active disease per 2018 iwCLL criteria) whilst on treatment, death, or end of the study.

In order to begin the initial ibrutinib pause in the pausing ibrutinib arm, all criteria below must be met and maintained continuously for preceding 12 months:

- No palpable lymph nodes and
- No palpable spleen, and
- ALC  $<5 \times 10^9/L$

Criteria to resume/ restart ibrutinib in 'pausing ibrutinib' arm:

Any one of:

[figure not shown]
- Palpable lymph nodes ( $\geq 2\text{cm}$ ), or
- palpable spleen, or
- ALC  $\geq 5 \times 10^9/L$ .

Criteria for subsequent ibrutinib pause(s) (second and subsequent pausing treatment breaks):

- Received at least a further 12 months of ibrutinib, and
- No palpable lymph nodes, and
- No palpable spleen, and
- $<5 \times 10^9/L$  ALC for at least 6 months.

# 4 FLOW DIAGRAM

## A Randomised Phase III Trial Comparing Intermittent with continuous Treatment Strategies in CLL

## 5 GLOSSARY OF TERMS

---

AE	Adverse event
ALT	Alanine aminotransferase
AR	Adverse reaction
BCRP	Breast cancer–resistance protein
BTK	Bruton’s tyrosine kinase
CHI Number	Community Health Index Number
CI	Chief Investigator
CLL	Chronic Lymphocytic Leukemia
CR	Complete response
CRi	Complete Remission with Incomplete Count Recovery
CRF	Case report form
CTA	Clinical Trials Authorisation
CTRU	Clinical Trials Research Unit
DMEC	Data Monitoring and Ethics Committee
DSUR	Developmental Safety Update Report
ECOG	Eastern Cooperative Oncology Group
eCRF	Electronic Case Report Form
EORTC	European Organisation for Research and Treatment of Cancer
GCP	Good Clinical Practice
G-CSF	Granulocyte colony stimulating factor
HMDS	Haematological Malignancy Diagnostic Service
ICD	Informed Consent Document
IMP	Investigational medicinal product
ITT	Intention to treat
LFT	Liver function test
MedDRA	Medical Dictionary for Regulatory Activities
mg	Milligram
MHRA	Medicines and Healthcare Products Regulatory Agency
MRD	Minimal Residual Disease
NCRI	National Cancer Research Institute
NICE	National Institute for Health and Care Excellence
OS	Overall survival
PD	Progressive disease
PFS	Progression-free survival
PI	Principal Investigator
PIS	Patient Information Sheet
PP	Per Protocol
PR	Partial remission
PS	Performance status
QoL	Quality of life
RDE	Remote Data Entry
REC	Research Ethics Committee
RSI	Reference Safety Information
SD	Stable disease
SAE	Serious adverse event

SAP	Statistical analysis plan
SAR	Serious adverse reaction
SmPC	Summary of Product Characteristics
SPM	Secondary Primary Malignancy
SSOP	Study site operating procedure
SUSAR	Suspected unexpected serious adverse reaction
TMG	Trial Management Group
TSC	Trial Steering Committee
TTP	Time to progression
U&E's	Urea & electrolytes
ULN	Upper limit of normal

## 6 BACKGROUND AND RATIONALE

---

### 6.1 Chronic Lymphocytic Leukaemia (CLL)

Chronic Lymphocytic Leukaemia (CLL) is the most common adult leukaemia, affecting 6.6 per 100,000 population (1). CLL is a chronic and currently incurable disease with a highly variable clinical course and can be associated with a range of symptoms including swollen glands, anaemia, fatigue and enlarged liver and spleen. Most patients will eventually require treatment and it is common for patients to receive several lines of therapy during the course of their disease (2).

### 6.2 Ibrutinib treatment for CLL

Ibrutinib is a small molecule inhibitor of Bruton's tyrosine kinase (BTK) that has dramatically improved the outcome in CLL (3, 4). Ibrutinib is licensed as continuous treatment given daily until disease progression in both previously untreated as well as relapsed, refractory CLL and is also approved for other similar chronic lymphoproliferative disorders, such as mantle cell lymphoma and Waldenstrom's macroglobulinaemia. Ibrutinib is currently commissioned within the NHS (5) for patients who have failed prior therapy for CLL, as well as for newly diagnosed patients with genetically high-risk disease.

### 6.3 Study Rationale

Ibrutinib is an extremely effective treatment for CLL with median progression-free survival (PFS) estimated to be 4 years in patients with a median of 3 prior lines of CLL therapy (4) and in excess of 10 years in newly diagnosed patients (3).

Ibrutinib is associated with long-term toxicities in a proportion of patients including arthralgia, bruising and bleeding, rashes and hypertension. Potentially serious side effects include cardiac arrhythmias, mostly atrial fibrillation but rarely ventricular tachyarrhythmias, and infections. It is hypothesised that toxicities may be reduced by an intermittent treatment approach.

A major concern with the chronic and continuous administration of ibrutinib is the selection of CLL sub-clones with BTK mutations leading to the development of disease resistance. Such BTK mutations are frequently observed in patients with relapsed/refractory CLL treated with ibrutinib and are also observed, but to a far lesser extent, in previously untreated patients receiving ibrutinib (6, 7). The emergence of these mutations is hypothesised to be reduced by intermittent use of the drug, as has been investigated using a similar strategy in prostate cancer (8).

We hypothesise that an intermittent treatment strategy with ibrutinib will reduce treatment-emergent resistance and thus be at least non-inferior to continuous treatment with regards to time to strategy failure whilst reducing resource impact for the NHS and improving quality of life. Recent work reveals the presence of BTK mutations is associated with drug resistance following continued treatment with ibrutinib in a third of patients with high risk CLL (9).

STATIC is designed with multiple pathways: the randomisation trial and the Clinical Need Cohort. The randomisation trial is designed to address the key question of whether an intermittent treatment

strategy with ibrutinib is at least as effective as the current licensed continuous treatment strategy. The justification for this question is that the trials that led to the approval of ibrutinib were all performed with relatively short follow-up. At the time of the first regulatory approval of ibrutinib in relapsed refractory CLL the pivotal randomised trial had a median follow-up of 9.4 months (10) and at the latest follow-up the median duration of treatment on ibrutinib was only 41 months (11). Similarly in previously untreated CLL the initial report of the RESONATE-2 trial had a median follow-up on ibrutinib of 18.4 months (3) and at the latest follow-up a median duration on treatment of 57.1 months (12). Therefore, the rationale of continuous treatment until active disease has not been studied. In addition, as it is now clear that continuous therapy with ibrutinib selects for CLL sub-clones with resistance mutations, such as the mutation of BTK, that occur in both previously treated and previously untreated CLL, although the rate and timing of mutations varies for front-line vs relapsed/refractory disease (6). Clonal evolution in CLL leads to therapy resistance and shorter remissions with subsequent treatments. Clearly relapse of CLL in patients currently receiving ibrutinib means that this drug, or class of drugs, will no longer be effective. In contrast it would be expected that recurrence of CLL in a patient not on ibrutinib would most likely be responsive to further ibrutinib. In addition to the clonal selection of continuous ibrutinib there are side effects of therapy which can have an impact on the patient's quality of life as well as potentially resulting in compliance issues. Some side effects can be life-threatening (13). Finally, it is becoming clear that when patients stop ibrutinib due to intolerance the disease frequently remains in remission not requiring therapy for potentially considerable periods of time. In the RESONATE-2 trial when patients stopped ibrutinib for intolerance, patients in complete response (CR)/ complete remission with incomplete count recovery (Cri) had a median PFS of 56 months and even those not in CR/Cri had a median PFS of 33 months. This suggests that disease control may persist for a period of time following pausing of ibrutinib treatment, and patients may continue to benefit for a meaningful period of time if they are paused when in good response. Finally the costs associated with continuous therapy until disease progression are not insignificant (14).

The strategy of intermittent treatment with a kinase inhibitor has been studied in chronic myeloid leukaemia (CML), a haematological malignancy treated with continuous oral tyrosine kinase inhibitors (TKI) such as imatinib. TKI treatment breaks in CML have been shown to be a safe and effective approach in this disease with no adverse impact on long-term disease control (15, 16). This precedent demonstrates the efficacy in haematological malignancies treated with an intermittent, as opposed to continuous TKI, which may translate to CLL treatment.

In the FLAIR trial (17) patients who still have detectable CLL after 3 years of ibrutinib-based therapy are scheduled to receive a total of 6 years of ibrutinib and then to stop treatment. It is likely that a proportion of patients will, at the end of 6 years, have a very low level of, or even undetectable, residual disease. There is a strong rationale, as explained above, for patients to consider entry into STATIC, given that patients randomised to intermittent ibrutinib will be carefully monitored and will be able to re-commence ibrutinib if their CLL begins to progress, with the expectation that many would be likely to respond upon restarting therapy.

Given that the efficacy of intermittent treatment is not proven, and continuous treatment with ibrutinib has demonstrated durable disease control in multiple studies, the Clinical Need Cohort affords patients who are concerned about pausing therapy a pathway to continue ibrutinib as it is licensed (continuous treatment) within STATIC.

## 7 AIMS AND OBJECTIVES

---

### 7.1 Aims

The primary aim is to assess whether patients with CLL on prior treatment with a BTK inhibitor, (including ibrutinib for 3 to 6 years) have disease control with an intermittent treatment strategy that is not inferior to disease control with the standard (licensed) continuous treatment.

### 7.2 Primary objectives

The primary objective is to assess non-inferiority (NI) of the intermittent treatment strategy in terms of time to treatment strategy failure, defined as the first documented instance of active disease (as defined by the 2018 iwCLL criteria) that does not respond to treatment, or death.

### 7.3 Secondary objectives

The secondary objectives are to assess:

1. Overall survival
2. Toxicity and tolerability
3. Cost effectiveness
4. Quality of life
5. Summative treatment-free Interval
6. Response to retreatment in intermittent treatment arm
7. Time to next treatment for CLL
8. Response to next treatment for CLL
9. Rate of resistance mutation between trial arms
10. Evolution of resistant sub-clones

#### 7.3.1 Hypothesis: Reduced Disease Resistance

We hypothesise that an intermittent treatment strategy using ibrutinib, will reduce treatment-emergent resistance and thus be at least non-inferior to continuous treatment with regards to time to treatment strategy failure whilst reducing resource impact for the NHS and improving quality of life.

### 7.4 Exploratory objectives

The exploratory objectives are:

- Analysis of the cause of ibrutinib resistance where BTK and/or PLC $\gamma$ 2 mutations are not found
- Identification of predictors for early progression of CLL after pausing ibrutinib
- Study of CLL clonal evolution in patients treated with ibrutinib
- Assessment of response to vaccines and rate of infectious complications

## 8 DESIGN

---

### 8.1 Overall design and plan of the study

The 'Randomisation Pathway' is designed as a prospective, multicentre, open-label, randomised, controlled, 2-arm, parallel-group, non-inferiority study to compare an intermittent treatment strategy (experimental arm) with continuous treatment (control arm) with ibrutinib for patients with CLL who have responded well to treatment with ibrutinib. The primary outcome for this pathway will be time to treatment strategy failure, defined as the first documented instance of active disease as defined by the 2018 iwCLL criteria (Appendix 1) that does not respond to treatment, or death from any cause.

At randomisation previously treated participants will have been receiving ibrutinib as their second- or subsequent-line of therapy for at least the previous 36 months, whilst front-line participants entering from the FLAIR trial will have received 6 years of treatment with ibrutinib. There is no restriction on maximum duration of treatment for the previously treated cohort prior to enrolment. The recruitment period is 6 years, and each participant will be followed up for at least 3 years after randomisation. Participants will receive treatment during the trials 6 year recruitment period and for the 3 years of follow up, meaning that participants will be on the trial for between 3-9 years, depending upon when they enter the trial. 800 patients will be entered into the Randomisation Pathway with the goal of observing 379 treatment failure or death events.

Participants will be randomised to either an intermittent treatment strategy or to continuous therapy. Treatment allocation (1:1) will be by minimisation with a random element incorporating the following three factors: centre, whether or not the participant was previously treated in FLAIR and minimal residual disease (MRD) level at randomisation.

Participants randomised to the intermittent treatment arm will pause ibrutinib treatment immediately following randomisation, and restart when the restart criteria are met (see Section 13.8.3; the restart criteria do not indicate active disease as per 2018 iwCLL criteria). When the re-start criteria are met participants will receive ibrutinib (oral) 420mg per day (or other reduced dose, if that dose has been stable for the past 6 months and there are no unresolved toxicities) until treatment failure (active disease per 2018 iwCLL criteria) whilst on treatment or death. If these participants demonstrate active disease whilst on the planned treatment pause they will initially resume ibrutinib and the criteria for treatment failure would be met if they present with active disease at the next follow up (in which case the time to treatment failure would be backdated to when active disease was first demonstrated). Those randomised to the continuous treatment arm will receive ibrutinib (oral) 420mg per day (or other reduced dose, if that dose has been stable for the past 6 months and there are no unresolved toxicities) until treatment failure (active disease) as per 2018 iwCLL criteria or death.

The Clinical Need pathway is a prospective, national, multicentre, open-label, single-arm, non-randomised cohort to assess the safety and overall survival of patients receiving continuous ibrutinib treatment. Participants exiting the FLAIR trial who are not eligible for randomised study because they have signs of progressive or returning CLL after completing 6 years of ibrutinib treatment within FLAIR, but prior to entry into STATIC, can join the Clinical Need Cohort. Participants in the Clinical Need Cohort

will receive treatment during the trials 6 year recruitment period and for the 3 years of follow up, meaning that participants will be on the trial for between 3-9 years, depending upon when they enter the trial. Up to 30 patients are expected to enter into the Clinical Need Cohort. Patients will continue receiving continuous ibrutinib, either at the standard dose, or a stable reduced dose.

Front-line participants entering either the Randomisation pathway or the Clinical Need cohort from the FLAIR trial should enter STATIC on completion of treatment in FLAIR, with no break in therapy, with the exception of participants who have completed the 6 years of treatment in FLAIR prior to STATIC opening.

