## **12.5 Treatment post-relapse/treatment failure**

Participants randomised to the pausing ibrutinib arm who demonstrate active disease will initially resume ibrutinib treatment. Participants who present with non-responsiveness to the reintroduction of ibrutinib as evidenced by continued active disease as per the 2018 iwCLL criteria, will meet the criteria of treatment failure and this should prompt the discontinuation of ibrutinib and consideration of subsequent therapy off-study at the discretion of the local investigator.

Participants randomised to the continuous ibrutinib arm who demonstrate active disease (see Appendix 1) at any time during the trial will meet the criteria of treatment failure and should be treated off-study at the discretion of the treating clinician.

Participants in the Clinical Need Cohort should continue to receive ibrutinib at the treating clinician's discretion until this is no longer providing benefit. Non-responsiveness to continued ibrutinib, as evidenced by symptomatic active disease, should prompt the discontinuation of ibrutinib and the participant should be treated off-study at the discretion of the treating clinician.

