### **13.10 Active Disease**

#### **13.10.1 Definition of Active Disease**

Participants will be evaluated for progression until the criteria of active disease is met, leading to the requirement to change to an alternative therapy (treatment failure). For participants randomised to the intermittent treatment arm the criteria of active disease must be met whilst the participant is on treatment.

Active disease, defined by the 2018 iwCLL criteria, is characterised by at least one of the following:

- Evidence of progressive marrow failure as manifested by the development of, or worsening of, anaemia and/or thrombocytopenia. Cut-off levels of Hb <10 g/dL or platelet counts <100 × 10^9/L are generally regarded as indication for treatment. However, in some patients, platelet counts <100 × 10^9/L may remain stable over a long period; this situation does not automatically require therapeutic intervention.
- Massive (i.e., ≥6 cm below the left costal margin) or progressive or symptomatic splenomegaly.
- Massive nodes (i.e., ≥10 cm in longest diameter) or progressive or symptomatic lymphadenopathy.
- Progressive lymphocytosis with an increase of ≥50% over a 2-month period, or lymphocyte doubling time (LDT) <6 months. LDT can be obtained by linear regression extrapolation of absolute lymphocyte counts obtained at intervals of 2 weeks over an observation period of 2 to 3 months; patients with initial blood lymphocyte counts <30 × 10^9/L may require a longer observation period to determine the LDT. Factors contributing to lymphocytosis other than CLL (e.g., infections, steroid administration) should be excluded.
- Autoimmune complications including anaemia or thrombocytopenia poorly responsive to corticosteroids.
- Symptomatic or functional extranodal involvement (e.g., skin, kidney, lung, spine).
- Disease-related symptoms as defined by any of the following:
  - a. Unintentional weight loss ≥10% within the previous 6 months.
  - b. Significant fatigue (i.e., ECOG performance scale 2 or worse; cannot work or unable to perform usual activities).
  - c. Fevers ≥100.5°F or 38.0°C for 2 or more weeks without evidence of infection.
  - d. Night sweats for ≥1 month without evidence of infection.

Hypogammaglobulinemia, or monoclonal or oligoclonal paraproteinemia does not by itself constitute a basis for initiating therapy. However, it is recommended to assess the change in these protein abnormalities, if patients are treated.

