## 17.4 Derivation of Endpoints

### 17.4.1 Time to Treatment Strategy Failure

Time to treatment strategy failure is defined as the time from randomisation to time of treatment strategy failure. Treatment strategy failure is defined as the first documented instance of active disease that does not respond to treatment, or death from any cause. If a participant reaches active disease whilst on a break and they continue to meet this criteria whilst on subsequent ibrutinib treatment, then the time of the event is when they first met the criteria for active disease. Individuals who are lost to follow-up, withdraw from all follow-up or continuing with their treatment strategy at the time of analysis will be censored at the date of last assessment. Participants who transfer to an alternate BTK inhibitor without experiencing active disease will be censored at their last assessment pre-transfer.

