## 18.1 Sample Size

As the primary endpoint will be evaluated for the Randomisation Pathway the sample size and recruitment rate calculations are based on participants entering this pathway.

In relapsed/refractory patients, the median PFS on ibrutinib is almost 4 years [7]. In treatment naive patients, the median PFS is estimated to be approximately 10 years [6]. We expect to be able to recruit ~45% of participants from FLAIR and ~55% from relapsed/refractory patients. We assume that PFS will be strongly related to the primary endpoint: time to treatment strategy failure. Assuming exponential distributions leading to a hyperexponential distribution, these medians combine to produce an overall median PFS of 5.84 years. We use PFS here as a surrogate for time-to-treatment strategy failure.

With a one-sided alpha of 2.5%, 80% power and allowing for 5% dropout, to detect a non-inferiority hazard ratio (HR) upper bound of 1.33 would require 379 events (using the continuous treatment arm as the reference). Accounting for those participants who will be lost-to-follow-up 800 patients (approximately 140/year) are planned to be randomised over a 6 year period, with the required number of events expected at approximately 3 years after the close of recruitment.

The highest HR point estimate that would lead to a result of non-inferiority is 1.08, based on a 95% confidence interval of (0.89, 1.33). This corresponds to the intermittent treatment strategy having an 8% extra risk of relapsing, or equivalently a 2.7% decrease in 5-year PFS probabilities (55.2% to 52.5%), with a range of a 9.3% decrease to a 3.3% increase. This reduction in PFS agreed to be clinically acceptable with the National Cancer Research Institute (NCRI) CLL subgroup, because of expected reduction in toxicity, increase in QoL, and the substantial potential for health care resource savings. In addition, there are good salvage therapies on progression, such as venetoclax which is approved for patients failing ibrutinib in the NHS, so a small impact on PFS would not be likely to translate to a difference in overall survival (OS).

We believe it is very likely that the intermittent strategy will actually be superior to continuous treatment in terms of PFS, because the treatment breaks may well delay the time to emergence of drug resistance (18, 19) as well as reducing long-term toxicities (20). If the experimental strategy is actually 5% better, the power increases to 90%.

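### The primary event is defined inconsistently and not on the same basis in both arms, which can favour non-inferiority by an unknown amount

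*Protocol*

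**What the plan says.** The endpoint derivation in protocol section 17.4.1 is common to both arms: "Treatment strategy failure is defined as the first documented instance of active disease that does not respond to treatment, or death from any cause". Sections 7.2 and 8.1 define it in the same terms. The operational text then diverges.

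- **Pausing arm, on a break.** Ibrutinib is resumed, and by section 8.1 "the criteria for treatment failure would be met if they present with active disease at the next follow up". Sections 12.5 and 13.8 say the same. A confirmed event is dated back to its first documentation (8.1, 17.4.1).
- **Pausing arm, on drug.** Section 13.10.1: "For participants randomised to the intermittent treatment arm the criteria of active disease must be met whilst the participant is on treatment". No second visit is asked for.
- **Continuous arm, first version.** Section 12.5 says that active disease "at any time during the trial will meet the criteria of treatment failure". Section 8.1 likewise treats active disease as failure without a response check.
- **Continuous arm, second version.** Section 13.8 counts failure only when active disease creates a need for a different therapy, as judged by the local investigator. Section 13.10.1 ties failure to the same need.

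The trial is open-label, response is assessed by the local clinician (section 16), and visits are every 3 months.

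**The concern.** Three conditions for the same event are in play: active disease alone, active disease that forces a change of therapy, and active disease that does not respond. Which one applies depends on the section read and, in part, on the arm.

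Two kinds of finding can be treated differently between arms. The first is an unconfirmed or transient finding. If it falls in a planned break and has gone by the visit after restart, it is dropped; in the continuous arm, under 8.1 and 12.5, it is an event. The second is a finding made off drug. Section 12.3.5 provides for surgical interruptions and section 17.4.6 expects toxicity breaks in the continuous arm. Under 12.5, active disease found then is a failure, whereas in the pausing arm the same off-drug state leads to re-testing.

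Removing such events mainly from the experimental arm lowers the hazard ratio, which is the anti-conservative direction here. Requiring non-inferiority in both the ITT and PP populations (section 19.3) does not help, because both use the same event definition.

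**Working it through.** **1. The plan's own figures.** Section 18.1 states: "With a one-sided alpha of 2.5%, 80% power and allowing for 5% dropout", and "to detect a non-inferiority hazard ratio (HR) upper bound of 1.33 would require 379 events". With 1:1 allocation, the required events are 4(1.960 + 0.842)² / (ln HR)². An HR of 1.33 gives 386.04, so 387; an HR of 4/3 gives 379.35. The stated 379 is reproduced to within about 2% and appears to come from 4/3. Section 18.1 also says that "these medians combine to produce an overall median PFS of 5.84 years". Solving 0.45·2^(−t/10) + 0.55·2^(−t/4) = 0.5 gives t = 5.84 years, as stated. None of these figures depends on the confirmation rule.

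**2. The rules side by side.**

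| Finding of active disease | Pausing arm | Continuous arm |
|---|---|---|
| On ibrutinib | Event (13.10.1) | Event (8.1, 12.5); only if therapy must change (13.8, 13.10.1) |
| Off ibrutinib, gone after restart | Not an event | Event under 12.5; not an event under the on-break sentence of 17.4.1 |
| Off ibrutinib, still present after restart | Event, dated to first documentation | Event |

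The arms clearly part in the second row. The first row differs only according to which continuous-arm text is followed.

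**3. Illustration of size.** From the protocol: control hazard λ = ln 2 / 5.84 = 0.1187 per year, 379 events, margin 1.33, one-sided 2.5%. The hazard is borrowed from PFS: "We use PFS here as a surrogate for time-to-treatment strategy failure". Assumed, because the protocol gives neither: transient findings arise at rate f per patient-year in both arms, and the pausing arm is on drug for a share d of the time. Every transient finding counts in the continuous arm, and only on-drug ones count in the pausing arm.

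- Observed HR at a true HR of 1.33 = (1.33λ + d·f) / (λ + f)
- SE(log HR) = 2/√379 = 0.1027
- P(non-inferiority) = Φ[(ln 1.33 − ln HR_obs)/0.1027 − 1.96]

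Worked case, f = 0.01 and d = 0.5: (0.1579 + 0.0050)/(0.1187 + 0.0100) = 1.266; P = 7.0%.

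| f per patient-year | d | Observed HR | P(non-inferiority) |
|---|---|---|---|
| 0 | any | 1.330 | 2.5% |
| 0.25% | 0.5 to 0.2 | 1.313 to 1.307 | 3.3% to 3.7% |
| 0.5% | 0.5 to 0.2 | 1.296 to 1.284 | 4.4% to 5.3% |
| 1% | 0.5 to 0.2 | 1.266 to 1.242 | 7.0% to 9.8% |
| 2% | 0.5 to 0.2 | 1.210 to 1.167 | 15% to 25% |

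The result is driven almost wholly by f, which is unknown. The calculation treats the test as a single look at 2.5%; section 19.3.1 uses 2.35% at the final analysis after an interim look.

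**4. What would cancel it.** Suppose judging failure at the first visit after restart creates false failures in the pausing arm at rate g per patient-year. The observed HR returns to 1.33 when 1.33λ + d·f + g = 1.33(λ + f), so g = f(1.33 − d). For f = 1%, g is 0.83% (d = 0.5) to 1.13% (d = 0.2) per patient-year. An opposite error of about the same size as f would therefore remove the effect.

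**The case against.** **The rule mostly follows drug status, not arm.** Active disease on ibrutinib is the failing finding in both arms, and the visit after restart is the first on-drug assessment. Not counting disease that responds to restart is the strategy question itself. Confirmed events are backdated, so the pausing arm gains no time. All this stands. It does not cover section 12.5, which follows the arm.

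**The on-break sentence of 17.4.1 names no arm,** so it can already cover a continuous-arm participant off drug. True, but 12.5 says otherwise. Section 12.4 requires consultation after an unplanned stop of more than 4 weeks, so these off-drug periods are generally short.

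**Under 13.8 and 13.10.1 a passing sign that prompts no change of therapy is not a failure.** Correct. A reader might infer that every single finding counts at once in the continuous arm; the documents support that only under 8.1 and 12.5. The conflict then becomes part of the point, since one version rests on unblinded local judgement.

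**Several criteria already filter transient findings.** Section 13.10.1 asks for sweats lasting at least a month, and lymphocytosis is assessed over time with other causes excluded. This stands and argues for a low rate. Fatigue carries no duration requirement, and treatment-related cytopenia could be misread as marrow failure.

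**The direction is not proved.** Appendix 1 (5.3.4) notes that kinase inhibitors can raise lymphocyte counts, and section 17.4.7 assesses response to re-treatment only at 9 to 12 months. A verdict at the first 3-monthly visit after restart could create false failures in the pausing arm. Appendix 1 also says that in such cases lymphocytosis alone is not failure, which limits this risk but does not remove it.

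**Conclusion.** The protocol defines its primary event in ways that conflict and do not rest on the same basis in both arms. Unconfirmed findings, and findings made off drug, can be dropped in the pausing arm and counted in the continuous arm. That can favour non-inferiority.

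The size is unknown. At assumed transient rates of 0.5 to 1% per patient-year, with the pausing arm assumed to be on drug 20 to 50% of the time, the false non-inferiority rate at a true HR of 1.33 would be about 4 to 10% instead of 2.5%. This is a scenario, not an estimate: it counts every transient finding in the continuous arm and sets false failures after restart to zero.

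A reader might infer that the trial is biased towards non-inferiority, or that its type I error is known to be inflated. The documents support neither: they give no rate of transient findings, the net direction is unproved, and re-challenge after a planned pause is a legitimate part of the strategy. What they do support is that the event needs a single definition, which matters in an open-label, locally assessed non-inferiority trial.

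**What to change.** Reconcile sections 8.1, 12.5, 13.8, 13.10.1 and 17.4.1 into one counting rule, stated in 17.4.1 and referred to elsewhere, that depends on drug status and not on arm:

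- Apply the on-break sentence of 17.4.1 to any participant off ibrutinib, in either arm and for any reason.
- For findings on ibrutinib, use the same confirmation standard in both arms: active disease still present at the next assessment, or another CLL therapy started.
- Keep death from any cause as an event, and date confirmed events to the first documentation of active disease.

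Add a sensitivity analysis that counts first documented active disease in both arms. It may sit in the SAP, so its absence from the protocol is not itself a fault. Settle the rule before the interim analysis at 190 events, which uses the same endpoint.

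This is a counting rule for the analysis only. It does not change when treatment is paused, resumed or replaced. The cost is protocol wording, one eCRF field, and some events confirmed up to one visit (3 months) later, with the event date preserved by back-dating. The target of 379 events is unchanged. One limit remains: where confirmation comes from starting another therapy, it still depends on open-label clinical judgement.
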